1.3. RATIONALE FOR THIS PHASE II EXPLORATORY TRIAL OF ZALYPSIS[®] IN EFT

[figure not shown]
Ewing's sarcoma is an aggressive neoplasm of the bone and soft tissues that arises primarily in adolescence and young adulthood. It is characterized by the occurrence of non-random gene rearrangements between the EWS gene on chromosome 22q12 with various members of the ETS gene family (20, 21). Although the introduction of chemotherapy has significantly improved the chance of survival of non-metastatic patients, shifting the 5-year survival rate to around 50–60% (22-24), in the last two decades the survival rate of Ewing's sarcoma patients has reached a plateau phase (25, 26). Particularly, limited improvement of survival rates has been achieved for metastatic and relapsed Ewing's sarcoma, with 5-year survival rates dropping to 13% in the latter; therefore, relapsed Ewing's sarcoma represents an unmet medical need.

There is evidence that sarcomas associated to translocations which deregulate transcription factors have high response rates to treatment with DNA binders such as trabectedin or Zalyps[®] compounds.

- Trabectedin has shown higher efficacy in the treatment of sarcomas having specific translocations producing deregulated transcription factors including FUS-CHOP myxoid/round cell liposarcoma (27-29) and Ewing's sarcoma (27, 30-32) although the specific mechanisms of action are still under investigation.
- Interestingly, they share TET-family genes (EWS or FUS) as gene fusion components. The fusion proteins contain a DNA binding domain and a transcriptional activation domain under the control of a constitutively expressed promoter that makes the fusion protein a deregulated transcription factor.
- Trabectedin has been described to impede the binding of FUS-CHOP fusion protein to some promoters regulated by the chimerical protein, interfering with the expression of downstream proteins (33).
- Both Zalyps[®] and trabectedin have been claimed to interfere with the transcriptional activity of EWS-FLI1, downregulating the expression of some EWS-FLI1 regulated genes such as NR0B1 (DAX1) (34).
- Zalyps[®] is a DNA binder that binds to DNA at the minor groove with a stronger effect in transcription regulation than in DNA repair as compared to trabectedin (7).
- Zalyps[®] shows an increased sensitivity compared to that of trabectedin in a panel of Ewing's sarcoma cell lines characterized by chromosomal translocations producing deregulated transcription factors (35). The effects of Zalyps[®] and trabectedin on growth inhibition are shown in [Figure 2](#).

[figure not shown]
- Zalypsis® increased sensitivity in the Ewing's sarcoma cell line panel is independent of the translocation/chimerical transcription factor variants. Wild-type p53 cell lines are more sensitive to trabectedin than to Zalypsis® (35) (see [Figure 3](#)).

Figure 2. Effects of Zalypsis® and trabectedin on growth inhibition.

Increased sensitivity in terms of growth inhibition IC₅₀ to Zalypsis® compared to trabectedin in a panel of Ewing's sarcoma cell lines containing specific chromosomal translocations.

Figure 3. Effects of Zalypsis® and trabectedin on p53 impact

Increased sensitivity in terms of p53 IC₅₀ to Zalypsis® compared to trabectedin in a panel of Ewing's sarcoma cell lines containing specific chromosomal translocations.

2. STUDY OBJECTIVES

2.1. PRIMARY OBJECTIVE

- To determine the antitumor activity of Zalyps[®] administered as a 1-h i.v. infusion on d1, d8 and d15, q4wk, to patients with advanced and/or metastatic EFT.

2.2. SECONDARY OBJECTIVES

- To determine time-to-event efficacy parameters.
- To characterize the safety profile and tolerability of Zalyps[®] in patients with unresectable advanced and/or metastatic EFT.
- To characterize the PK of Zalyps[®] when administered as a single-agent to patients with EFT.
- To determine the pharmacodynamic profile by measuring the effect of Zalyps[®] on the number of Ewing's sarcoma CTCs at different times of treatment and its correlation with the clinical outcome.
- To determine the PGx profile. Hypothesis-generating exploratory PGx analyses will be conducted to correlate the molecular parameters found in the tumor and blood samples of the patients with the clinical results achieved with Zalyps[®].

3. OVERALL STUDY DESIGN

This is a multicenter, open-label, single-arm, non-comparative, phase II clinical trial with single-agent Zalyps[®] given as a 1-h i.v. infusion on d1, d8 and d15, q4wk, to patients with advanced and/or metastatic EFT who failed to standard chemotherapy.

The primary endpoint of the study is the overall response rate (ORR), defined as the percentage of patients with objective response (OR), either complete response (CR) or partial response (PR), as defined by the Response Evaluation Criteria in Solid Tumors (RECIST) v1.1.

The study will consist of two stages. If in the first stage there are no responders after testing the drug on 12 evaluable patients, the trial will be terminated. If there are ≥ 1 responders the trial will go on to the second stage and 17 additional evaluable patients will be accrued. A total of 29 evaluable patients will be studied. If the total number of responders is ≤ 2 , the drug will be considered as not interesting in the setting of patients treated for this disease with this schedule.

Treatment will be administered in the absence of disease progression and/or unacceptable toxicity. In case of obtaining a CR, two additional cycles will be administered and then the treatment will be stopped.

A disease evaluation will be performed at baseline and every other cycle (± 1 week) until evidence of disease progression.

Patients will be evaluated using clinical and laboratory assessments before and after each treatment cycle. Any treatment-related AEs will be followed-up until the events or their sequelae resolve or stabilize at a level acceptable to the Investigator and the Sponsor(s). Patients no longer receiving study treatment will be followed up for survival (see Section [5.2](#)).

4. SELECTION OF PATIENTS

4.1. INCLUSION CRITERIA

In order to be included into the trial, patients have to fulfill all of the following criteria:

1. Voluntary written informed consent, obtained from the patient or his/her representative before the beginning of any specific study procedures.
2. Age ≥ 16 years.
3. Histologically or cytologically confirmed EFT, with recurrent disease.
4. Documented failure to at least one prior chemotherapy regimen for their disease.
5. Radiographic documentation of disease progression at study entry.
6. Eastern Cooperative Oncology Group (ECOG) performance status (PS) score ≤ 2 .
7. Life expectancy ≥ 3 months.
8. Complete recovery from the effects of drug-related AEs derived from previous treatments, excluding alopecia and grade 1 peripheral neuropathy, according to the NCI-CTCAE v. 4.0.
9. At least one measurable lesion ("target lesion" according to the RECIST v. 1.1), located in a non-irradiated area and adequately measured less than four weeks before study entry. Tumors within a previously irradiated field will be designated as "non-target" lesions unless progression is clearly documented or biopsy proven.
10. Absolute neutrophil count (ANC) $\geq 1.5 \times 10^9/l$; platelet count $\geq 100 \times 10^9/l$, and hemoglobin ≥ 9 g/dl.
11. Adequate renal function: calculated creatinine clearance (using Cockcroft and Gault's formula) ≥ 30 ml/min.
12. Adequate hepatic function:
 - a) Total bilirubin $\leq 1.5 \times$ upper limit or normality (ULN), unless due to Gilbert's syndrome.
 - b) Alanine aminotransferase (ALT), aspartate aminotransferase (AST) $\leq 3 \times$ ULN ($\leq 5 \times$ ULN in case of hepatic metastases), and alkaline phosphatase (AP) $\leq 2.5 \times$ ULN ($\leq 5 \times$ ULN in case of extensive bone involvement).
 - c) Albumin ≥ 25 g/l.
13. Left ventricular ejection fraction (LVEF) within normal limits (LVEF of at least 50%).
14. Women of childbearing potential must have a negative serum pregnancy test before study entry. Both women and men must agree to use a medically acceptable method of contraception throughout the treatment period and for three months after discontinuation of treatment. Acceptable methods of contraception include complete abstinence, intrauterine device (IUD), oral contraceptive, subdermal implant and double barrier (condom with a contraceptive sponge or contraceptive suppository).

4.2. EXCLUSION CRITERIA

Patients fulfilling any of the following criteria will not be included into the trial:

1. Prior therapy with Zalayspis®.
2. Pregnant or lactating women or women of childbearing potential not using an appropriate contraceptive method.
3. Less than three weeks from prior radiation therapy, biological therapy or chemotherapy.
4. Less than six weeks from prior nitrosourea, mitomycin C, high-dose chemotherapy or radiotherapy involving the whole pelvis or over 50% of the spine, provided that acute effects of radiation treatment have resolved ([Appendix 2](#)). Hormonal therapy and palliative radiation therapy (i.e., for control of pain from bone metastases) must be discontinued before study entry.
5. Patients with a prior invasive malignancy (except non-melanoma skin cancer and *in situ* cervix carcinoma) who have had any evidence of disease within the last five years or whose prior malignancy treatment contraindicates the current protocol therapy.
6. Evidence of progressive or symptomatic central nervous system (CNS) metastases or leptomeningeal metastases.
7. Other diseases or serious conditions:
 - a) Increased cardiac risk, as defined by:
 - Unstable angina or myocardial infarction within 12 months before inclusion in the study.
 - New York Heart Association (NYHA) grade II or greater congestive heart failure.
 - Symptomatic arrhythmia or any arrhythmia requiring ongoing treatment.
 - Abnormal ECG, i.e., patients with the following are excluded: QT prolongation - QTc > 480 msec; signs of cardiac enlargement or hypertrophy; bundle branch block; partial blocks; signs of ischemia or necrosis, and Wolff Parkinson White patterns.
 - History or presence of valvular heart disease.
 - Uncontrolled arterial hypertension despite optimal medical therapy.
 - Previous mediastinal radiotherapy.
 - Previous treatment with doxorubicin at cumulative doses exceeding 400 mg/m².
 - b) History of significant neurological or psychiatric disorders.
 - c) Active infection requiring systemic treatment.
 - d) Significant non-neoplastic liver disease (e.g., cirrhosis).
 - e) Known hepatitis B virus (HBV) or hepatitis C virus (HCV) infection.
 - f) Immunocompromised patients, including those known to be infected with the human immunodeficiency virus (HIV).
 - g) Uncontrolled (i.e., requiring relevant changes in medication within the last month or hospital admission within the last three months) endocrine diseases (e.g., diabetes mellitus, hypo- or hyperthyroidism, adrenal disorder).
8. Any other major illness that, in the Investigator's judgment, will substantially

increase the risk associated with the patient's participation in the study. The Investigator should feel free to consult the Study Coordinator or the Sponsor(s) for uncertainty in this regard.

9. Limitation of the patient's ability to comply with the treatment or to follow-up at a participating center. Patients enrolled into this trial must be treated and followed at a participating center.
10. Treatment with any investigational product within 30 days prior to inclusion in the study.
11. Known hypersensitivity to any component of Zalypsia®.

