Pharmacodynamic and pharmacogenomic substudy inclusion criteria	
 • All patients included in trial PM104-B-003-10 will be eligible. • Only those patients who have themselves or their representatives voluntarily signed the Informed Consent Form for the PGx study will participate.
EXCLUSION CRITERIA	
 1. Prior therapy with Zalypsis®. 2. Pregnant or lactating women or women of childbearing potential not using an appropriate contraceptive method. 3. Less than three weeks from prior radiation therapy, biological therapy or chemotherapy. 4. Less than six weeks from prior nitrosourea, mitomycin C, high-dose chemotherapy or radiotherapy involving the whole pelvis or over 50% of the spine, provided that acute effects of radiation treatment have resolved. Hormonal therapy and palliative radiation therapy (i.e., for control of pain from bone metastases) must be discontinued before study entry. 5. Patients with a prior invasive malignancy (except non-melanoma skin cancer and in situ cervix carcinoma) who have had any evidence of disease within the last five years or whose prior malignancy treatment contraindicates the current protocol therapy. 6. Evidence of progressive or symptomatic central nervous system (CNS) metastases or leptomeningeal metastases. 7. Other diseases or serious conditions: 
 a) Increased cardiac risk, as defined by: 
 • Unstable angina or myocardial infarction within 12 months before inclusion in the study. • New York Heart Association (NYHA) grade II or greater congestive heart failure. • Symptomatic arrhythmia or any arrhythmia requiring ongoing treatment.

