5.5. PRE-TREATMENT EVALUATION

During the pre-treatment period, and once the patient or his/her representative has signed the Informed Consent Form, the Investigator will confirm the patient's eligibility for the study by conducting the following assessments (Table 5).

Additional information on the collection and processing of pharmacodynamic and PGx samples will be provided as a separate document in the “Guide for Identification, Packaging and Shipment of Pharmacodynamic and Pharmacogenomic Samples”.

Table 5. Pre-treatment assessments

	PRE-TREATMENT ASSESSMENT	TIME
1. History and clinical examination	
 Written informed consent. Medical history: 
 Date of diagnosis of the primary disease. Demographic information (race/ethnicity, age). Prior treatments (surgery, radiotherapy, chemotherapy, immunotherapy), specifying the best response and the date of PD. Concomitant diseases and treatments. Weight, height and BSA. Complete physical examination. Vital signs: heart rate, blood pressure and body temperature. ECOG PS (Appendix 1). 	Prior to any specific study procedures. All within four weeks prior to Day 1 of Cycle 1. Complete physical examination, ECOG PS, vital signs, and weight must be repeated on Day 1 of Cycle 1, prior to administration of the first Zalyps [®] infusion.
	
 ECG* LVEF* by ECHO. 	Within four weeks prior to Day 1 of Cycle 1; ECG must be repeated on Day 1 of Cycle 1, before the administration of the first Zalyps [®] infusion.
2. Laboratory tests	
 Hematology: differential WBC (neutrophils, lymphocytes), hemoglobin and platelets. Biochemistry A: liver function tests (ALT, AP, AST, LDH, total bilirubin), creatinine, CPK, troponin I*, glucose, and serum electrolytes (Na⁺, Cl⁻, K⁺, Ca⁺⁺, Mg⁺⁺). Biochemistry B: total protein and albumin. 	All within one week prior to Day 1 of Cycle 1. Repeat Hematology and Biochemistry A on Day 1 of Cycle 1 prior to treatment with Zalyps [®] (a window of -2 days allowed), if the treatment is administered more than one week after the pre-treatment test. Repeat Biochemistry B on Day 1 of Cycle 1 whenever clinically indicated.
3. Calculated creatinine clearance	Calculated according to Cockcroft and Gault's formula (Appendix 4).	Within one week prior to Day 1 of Cycle 1. Repeat on Day 1 of Cycle 1 whenever clinically indicated.

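### Exclusion 4 is worded the wrong way round: at three to under six weeks after whole-pelvis or over-50%-spine radiotherapy it bars the recovered patient and does not bar the unrecovered one

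*Protocol*

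**What the plan says.** Protocol section 4.2 opens with "Patients fulfilling any of the following criteria will not be included into the trial", so each item describes someone who stays out. Two items concern the timing of radiotherapy:

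- Exclusion 3: "Less than three weeks from prior radiation therapy, biological therapy or chemotherapy".
- Exclusion 4 sets a six-week limit. It covers three drug categories (high-dose chemotherapy, mitomycin C and nitrosourea) and also this one: "radiotherapy involving the whole pelvis or over 50% of the spine, provided that acute effects of radiation treatment have resolved". It points to Appendix 2.

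The synopsis version of exclusion 4 carries the same proviso, "provided that acute effects of radiation treatment have resolved". Appendix 2 only tabulates the percentage of marrow lying in standard radiation ports. It sets no recovery rule.

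Other provisions that bear on the point:

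- Inclusion 8 (section 4.1): "Complete recovery from the effects of drug-related AEs derived from previous treatments". Radiation effects are not named.
- Inclusion 10: ANC of at least 1.5 and platelets of at least 100 (×10⁹/l), and haemoglobin of at least 9 g/dl.
- Exclusion 8: "Any other major illness that, in the Investigator's judgment, will substantially" raise the patient's risk. This is discretionary.
- Section 5.5, Table 5: "Complete physical examination, ECOG PS, vital signs, and weight must be repeated on Day 1 of Cycle 1". No recovery threshold is attached.
- Section 7.2.3(g): a grade limit on other non-haematological toxicities, applied to re-treatment from Day 8 of Cycle 1.

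**The concern.** In an exclusion list, a proviso narrows the group that is kept out. Here it narrows that group to patients who have recovered, which is the opposite of what a recovery clause is for. A site that follows the text exactly could give the first infusion to a patient with unresolved acute effects of a large pelvic or spinal field, while turning away a recovered patient at the same interval.

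The situation is plausible in this disease. Protocol section 1.1 gives 26% of primaries as pelvic and 6% as spinal, and section 1.1.1 includes radiotherapy in standard management. These are shares by site, not counts of recent large-field treatment. At the trial dose, section 1.2.5.1.1 reports related nausea in 87.5% and vomiting in 83.3% of patients, so unresolved bowel effects from a pelvic field would be an unwelcome starting point.

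The analysis is touched as well. SAP section 7.1 tabulates eligibility deviations by criterion. Under the literal text the unrecovered patient would not be listed, while a recovered patient enrolled on an 'unless resolved' reading would be. SAP section 4.1.1 makes eligibility a condition of the efficacy population, so the reading adopted can decide whether such a patient counts among the 12 or the 29.

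**Working it through.** The plan gives no figure on this point, so the check is one of logic. It covers large-field radiotherapy only (whole pelvis or over 50% of the spine).

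**Inputs.** Let *t* be weeks since that radiotherapy and R mean that acute effects have resolved. A patient is excluded if exclusion 3 or exclusion 4 is met.

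- Exclusion 3: *t* < 3.
- Exclusion 4 as written: *t* < 6 and R.

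The intended rule is not stated, so three candidates are compared with the text:

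- Rule a, six weeks waived on recovery: *t* < 6 and not R.
- Rule b, six weeks and recovery both required for entry: *t* < 6 or not R.
- Rule c, a flat six-week washout: *t* < 6.

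**Result** (E = excluded, N = not excluded, with exclusion 3 applied throughout):

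| Weeks | Acute effects | As written | Rule a | Rule b | Rule c |
|---|---|---|---|---|---|
| <3 | resolved | E | E | E | E |
| <3 | unresolved | E | E | E | E |
| 3 to <6 | resolved | E | N | E | E |
| 3 to <6 | unresolved | **N** | E | E | E |
| ≥6 | resolved | N | N | N | N |
| ≥6 | unresolved | N | N | E | N |

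Cells where the text differs from the candidate rule:

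- Rule a: 2 of 6 (3 to <6 weeks, both rows).
- Rule b: 2 of 6 (unresolved at 3 to <6 weeks and at ≥6 weeks).
- Rule c: 1 of 6 (unresolved at 3 to <6 weeks).

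The cell for unresolved effects at 3 to <6 weeks is wrong under all three. The resolved cell in that window is wrong only under rule a.

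**Does another rule close the gap before the first infusion?**

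- Inclusion 10 largely covers marrow effects. Its limits are stricter than those for re-treatment in section 7.2.3 (ANC 1.5 against 1.0, platelets 100 against 75, ×10⁹/l).
- Inclusion 8 is confined to drug-related events.
- Exclusion 8 depends on the investigator's judgment.
- The Day 1 examination may reveal an effect but requires nothing to follow from it.
- Section 7.2.3(g) starts at the second infusion.
- The sponsor's eligibility check at registration (section 5.6) works from these same criteria.

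None of these expressly requires recovery from non-haematological acute radiation effects before the first dose.

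**Design figures.** The two-stage operating characteristics depend on the stage sizes, the cut-offs and the two response rates. None of these changes.

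**The case against.** The strongest reply is that only one outcome is certainly wrong. If a full six-week washout was meant, with or without recovery, barring the recovered patient at three to under six weeks is correct. That is so, and it limits the certain error to the unrecovered patient in that window. The ≥6-week cell under rule b likewise comes from the six-week limit rather than from the proviso.

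A second argument is that the reference to Appendix 2 suggests the worry was marrow, which inclusion 10 tests at entry. That is a fair inference, but the proviso speaks of acute effects generally.

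Third, other safeguards leave little exposure: performance status, organ-function limits, the active-infection exclusion, exclusion 8, the registration check and the Day 1 examination. From Day 8, section 7.2.3(g) would arguably stop a persisting effect of grade 2 or more, except grade 2 asthenia. These points reduce the expected harm and confine it mainly to the first infusion, but none is a radiation-recovery rule.

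Fourth, the sensitivity analysis in all treated patients (SAP section 7.3, Table 11.2.1.5) means that such a patient appears in the results whichever reading is used. This softens the reporting consequence but does not settle who belongs in the main analysis.

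Relying on sites to see the intent is not enough, because the plausible intentions disagree about a recovered patient at four weeks and at least six centres are planned. Protocol section 5.2.2 also places eligibility departures among the deviations that may affect risk/benefit, which as a general rule are not to be authorised.

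**Conclusion.** The concern holds. Exclusion 4 is wrong as written in both section 4.2 and the synopsis. At three to under six weeks after large-field radiotherapy it excludes the recovered patient and does not exclude the unrecovered one. The second result is wrong under every plausible intention; the first is wrong only if recovery was meant to waive the six weeks.

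The size is one or two of six time-by-recovery cells. That is a count of logical cases, not of patients. The number of patients cannot be derived from the documents and is probably small. The conclusion assumes a literal reading of the list and concerns non-haematological acute effects, mainly at the first infusion. The error rates and sample size of the two-stage design are not affected. The clause should be corrected because it is a safety eligibility rule that misdirects a site following it.

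**What to change.** Split exclusion 4 in section 4.2 and in the synopsis so that the recovery clause attaches only to large-field radiotherapy.

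- **4a:** nitrosourea, mitomycin C or high-dose chemotherapy within the previous six weeks.
- **4b:** one of two explicit rules, with the sponsor stating which it intends:
  - **(a)** whole-pelvis or over-50%-spine radiotherapy within the previous six weeks, unless its acute effects have resolved; or
  - **(b)** whole-pelvis or over-50%-spine radiotherapy within the previous six weeks, or any such radiotherapy whose acute effects have not resolved.

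Both exclude the unrecovered patient at three to under six weeks. They differ in two cells: the recovered patient in that window (admitted under a, excluded under b) and the unrecovered patient at six weeks or later (not excluded under a, excluded under b). Option (b) is the safer choice, because only it requires recovery from large-field treatment at any interval. The rules for small-field and palliative radiotherapy stay as they are.

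The cost is a wording amendment in two places, with no added procedures. Option (a) makes some recovered patients newly eligible. Option (b) may lose a few patients whose effects persist at six weeks or beyond, and it keeps recovered patients at three to under six weeks excluded, as the literal text does now.
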